Serious AEs include any events resulting in death, decreased life expectancy, life-threatening situations, persistent or permanent disability/incapacity, hospitalization, or congenital anomaly/birth defect or other important medical event. Within 24 hours, the Investigator will submit a written report documenting the circumstances of the serious AE.

While AE's and SAE's are not anticipated, should an incident occur during the visit or a subject report an event following the visit, the AE will be recorded in the subject's study records and followed to resolution.

12. Contacts and Locations

The subjects will randomly be recruited at clinical settings that deal with oral health, like dental or head and neck clinics. The outcome measure will be performed in this setting. Data will be collected on-site by the clinical staff.

13. Task Analysis

The Task Analysis breaks down the device use process into discrete sequences of tasks. The tasks will be analyzed to identify the user interface components involved, the use errors that users could make and the potential results of all use errors. The following task analysis is planned:

Phase	#	Task
I	1	Potential user knows the intended use of the study product.
	2	Potential user assesses correctly whether the study product is indicated for him/her.
	3	Potential user assesses correctly whether he/she can use the study product or not or conditioned to a medical advice.
II	1	User knows the maximum amount of times and the maximum length of time he/she can use the study product.
	2	User knows how to switch the study product ON and OFF.
	3	User knows how to place the study product into his/her mouth.
	4	User knows how to remove the study product from his/her mouth.
	5	Patient knows how to separate the intraoral and the extraoral units.
	6	Patients reports any significant discomfort felt with SaliPen
	7	Patients reports any significant difficultis in using SaliPen

Each task will be evaluated by the binary grading scheme satisfactory/unsatisfactory. The evaluator will be a member of the study team.

For Phase I - 100% success is needed to pass the evaluation for every subject.

For Phase II - 85% success rate is needed to pass the evaluation for every subject.

The Human Factor Study will be considered successful if 85% of the participants passed each Phase of the test.

14. Ethical and Legal Aspects

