14.5. Subject Confidentiality

All subject data will be identified only by a subject identification number and date of birth.

15. Guide for participants

Phase I - Self-Administered Questionnaire

I.D.: _____ DATE: _____

Please read the cover and the back cover of the device and answer the following questions:

1. Is the device for Dry Mouth Relief?

- Yes
- No

2. Does the device fit your needs?

- Yes
- No

3. If the device fits your needs, please check a box (only one):

- I can use the device.**
- I cannot use the device because, either:**
 - I'm under 18 years of age.
 - I suffer from epileptic disorder.
 - I'm allergic to gold or silicone rubber.
- I need a professional consultation before buying the device because, either:**
 - I use a pacemaker.
 - I'm pregnant.
 - I suffer from a psychiatric or psychological disorder.
 - I suffer from an involuntary movement disorder (for example Parkinson's disease).
 - I have a neurologic disorder in the head and neck area (for example trigeminal neuralgia).

Phase II - Interviewer-administered questionnaire

I.D.: _____ DATE: _____

Please read the user manual and hold the device.

Firstly, your oral cavity will be examined.

Next, you will be asked the following questions and to perform the following tasks:

- 1. How many times can you use the device in a day and how many minutes (maximum time) you can use the device in one session? (See page 2)**
- 2. How do you turn ON and OFF the device? (See page 6)**
- 3. How do you insert the device in your mouth? (See pages 7, 8 and 9 and watch the video “How to use the SaliPen device to stop dry mouth”)**
- 4. How do you take the device out of your mouth? (See pages 7, 8 and 9)**
- 5. How do you detach and reattach the white extraoral command unit from the blue intraoral stimulating unit? (See page 6)**
- 6. Did you experience discomfort with the SaliPen in your mouth?**
- 7. Did you experience difficulties in using the SaliPen?**

Finally, your oral cavity will be examined again.

16. Evaluation Sheets

Phase I

Subject I.D.: _____

EVALUATOR NAME: _____

Date: _____

Step 1: Anamnesis taken by the evaluator

Ruling	Parameters	yes	no
Indication	Xerostomia		
Contraindications	Under 18 years old		
	Epileptic disorder		
	Allergy to gold		
	Allergy to silicone		
Precautions – medical advice recommended before purchase	Pacemaker		
	Pregnant		
	Psychiatric or psychological disorder		
	Involuntary movement disorder (e.g., Parkinson's disease)		

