Gingival Mucosa			_____
Edentulous Ridge/Retromolar area			_____
Tongue			_____
Sublingual Area/floor of mouth			_____
Submandibular area			_____

Step 2: Assessment of subject performance
EVALUATOR NAME: _____

DATE: _____

Please evaluate how the participant addresses the following questions/tasks:

Questions	Participant's answer	Correct answer	Success (1) / Failure (0)
1. How many times in a day and how many minutes (maximum time) you can use the device in one session?			
Tasks	Evaluation		Success (1) / Failure (0)
2. How do you turn on ON and OFF the device?			
3. How do you insert the device in your mouth?			
4. How do you take the device out of your mouth?			
5. How do you detach and reattach the white extraoral command unit from the blue intraoral stimulating unit?			
Subject assessment (place an x where relevant for you) Note: Success (1) is meant if options 2 or 3 were chosen Failure (0) is meant if option 1 was chosen			Success (1) / Failure (0)
6. Did you experience discomfort with the SaliPen in your mouth?	1- Severe discomfort 2- Moderate discomfort 3- No discomfort		
7. Did you experience difficulties in using the SaliPen?	1- Severe discomfort 2- Moderate discomfort 3- No discomfort		

Summary evaluation:
Total questions/tasks/self-assessments: 7

Number of points: _____

Passed? (minimum 6 points):

Yes
 No

Step 3: Oral soft tissue examination

EVALUATOR NAME: _____

DATE: _____

	Normal	Abnormal	If Abnormal, please specify findings
Labial Mucosa (including lips)			
Buccal Mucosa			
Mucogingival Folds			
Gingival Mucosa			
Edentulous Ridge/Retromolar area			
Tongue			
Sublingual Area/floor of mouth			
Submandibular area		

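### Phase II items 6 and 7: as section 16 is written, the subject marks the self-rating under a heading that prints which answers score as success and failure, and section 15 describes a different mode of answering

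*Combined protocol and SAP*

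**What the plan says.** Section 16, Evaluation Sheets, Phase II Step 2, is laid out for the evaluator. It has an evaluator name line and opens with "Please evaluate how the participant addresses the following questions/tasks". Section 13 says of that person: "The evaluator will be a member of the study team".

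For items 6 and 7 the addressee changes. The heading reads "Subject assessment (place an x where relevant for you) Note: Success (1) is meant if options 2 or 3 were chosen", and then "Failure (0) is meant if option 1 was chosen". Each item offers three options, of which option 1 is severe, 2 is moderate and 3 is none. The scoring column stands beside them.

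Both items enter the subject's score: "Total questions/tasks/self-assessments: 7", then "Passed? (minimum 6 points". Section 13 sets the same threshold as 85% per subject and calls the study successful if 85% of participants pass each phase. Section 6 plans 16 participants for Phase II.

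Section 15, the participant guide, lists the same two items as bare questions, for example "Did you experience discomfort with the SaliPen in your mouth", with no answer options and no key. Its title for this part is "Phase II - Interviewer-administered questionnaire".

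**The concern.** A self-rating should be given without sight of how it will be scored. Here the instruction to mark the box and the key for the boxes share one heading, and no other form carries the options. Followed literally, the sheet tells respondents that severe is the failing answer at the moment they choose. The study is open label and the rating is given in front of study staff, so any pressure from the key would run one way, from severe towards moderate.

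At stake are the two scored self-ratings of discomfort and difficulty and, through them, the Phase II pass count. The conflict between sections 15 and 16 adds to this: subjects could be handled differently depending on which section the evaluator follows, and the records would not show which.

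**Working it through.** **1. Thresholds.** Inputs: 7 items and pass mark 6 (section 16); 85% at both levels (section 13); 16 participants (section 6).

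- Subject level: 0.85 × 7 = 5.95, rounded up to 6. This reproduces the sheet's pass mark (6/7 = 85.7%; 5/7 = 71.4% fails).
- Phase level: 0.85 × 16 = 13.6, rounded up to 14 (14/16 = 87.5%; 13/16 = 81.3% falls short).
- Weight of items 6 and 7: 2/7 = 28.6% of the points.

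**2. When a changed answer matters for a subject.** Score = performance items correct (of 5) + 2 − number of severe ratings.

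| Items 1–5 correct | No severe | One severe | Two severe |
|---|---|---|---|
| 5 | 7, pass | 6, pass | 5, fail |
| 4 | 6, pass | 5, fail | 4, fail |
| 3 or fewer | 5 or less, fail | fail | fail |

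Moving one rating from severe to moderate turns a fail into a pass in two cells: 5 correct with two severe, and 4 correct with one severe. With 4 correct and two severe, both ratings must move. Elsewhere the result stays the same; in particular, a subject with no use error and one severe rating passes either way.

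**3. When it matters for the phase.** One such subject changes the conclusion only if the count would otherwise be exactly 13, so that it becomes 14. Two such subjects would do so from 12, and so on.

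**4. Sensitivity of the success rule to these items.** The documents give no success rates, so these are assumptions: each of items 1–5 is satisfactory with probability p, each of items 6 and 7 is not severe with probability q, and all items are independent. With X ~ Binomial(5, p):

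P(subject passes) = q² · P(X ≥ 4) + 2q(1 − q) · P(X = 5)

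P(phase succeeds) = P(Binomial(16, P(subject passes)) ≥ 14)

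At p = 0.90, P(X = 5) = 0.59049 and P(X ≥ 4) = 0.32805 + 0.59049 = 0.91854.

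- q = 0.80: 0.64 × 0.91854 + 0.32 × 0.59049 = 0.777; phase 0.273
- q = 0.90: 0.81 × 0.91854 + 0.18 × 0.59049 = 0.850; phase 0.563
- q = 1.00: 0.919; phase 0.864

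P(phase succeeds) across the range:

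| p | q = 0.80 | q = 0.90 | q = 1.00 |
|---|---|---|---|
| 0.80 | 0.012 | 0.050 | 0.167 |
| 0.85 | 0.070 | 0.214 | 0.495 |
| 0.90 | 0.273 | 0.563 | 0.864 |
| 0.95 | 0.669 | 0.906 | 0.995 |

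The table shows that the success rule responds to these two items. It does not estimate the effect of the printed key: moving from q = 0.80 to q = 1.00 would mean that every severe rating was suppressed.

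**5. The two sections side by side.** Section 15 has an interviewer ask the questions and prints no options. Section 16 has the subject mark an option on a sheet otherwise addressed to the evaluator. Nothing says which governs, who holds the sheet, or that the key is covered. Phase I is laid out differently: its participant page in section 15 prints the answer options without scoring columns, and those columns appear only on the evaluator's sheet in section 16.

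**The case against.** The strongest reply is that Phase II is interviewer-administered by title, in contrast to the self-administered Phase I questionnaire, and that the Step 2 sheet belongs to the evaluator. On that reading the evaluator holds the form, asks the questions and records the answers, and the subject need never see the key. This stands as a limit: exposure is certain only if section 16 is followed as written. It does not settle the matter, because the instruction in section 16 is addressed to the person who felt the discomfort, and nothing says that section 15 prevails. Even under the interviewer reading, an unmasked member of the study team elicits the rating with the key in view.

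It is also fair that the boundary cases in the working are narrow and that the documents give no rate of severe ratings.

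A reader might infer more than the text supports:

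- That subjects see their own grades for items 1–5 before rating. The scoring column is in the same table, but nothing says that it is filled in by then or shown to them.
- That payment or keeping the device drives the answers. The synopsis ties payment to participation and offers the device to Phase II participants; neither depends on passing.
- That these are the only patient reports of tolerability or difficulty. Section 5.2 also provides for questions on product use and ease of use and for subjects to report discomfort, and section 11 provides for recording adverse events. Items 6 and 7 are only the scored self-ratings.

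**Conclusion.** The point holds as a cheap improvement to the forms. The mode of answering is contradictory between sections 15 and 16, and under section 16 as written the scoring key is in front of the respondent for 2 of the 7 points. The plausible direction is away from severe, since option 1 is the only one that scores zero.

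The size is unknown. A subject's result changes only at the pass boundary, and the phase result only near 14 of 16; the step from 13/16 to 14/16 illustrates that boundary and is not a forecast. The probabilities in the working rest on assumed p and q and on independence between items. A reader might conclude that the Phase II pass rate is in fact inflated. The documents do not show that: they show a form that can bias the rating, with no information on how often it would.

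**What to change.** State one mode of answering for items 6 and 7 in both section 15 and section 16. Give the subject these two items with their answer options on a page that carries neither the success/failure note nor the scoring column, as the Phase I participant page already does. Keep the key on the evaluator's sheet, and have the evaluator enter the score only after the answer has been recorded. If the interviewer mode is retained, the questions and options can be presented from the same key-free page.

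The cost is a form revision with IRB approval under section 14.4, plus one transcription step and its small risk of copying error. No extra subjects, visits or staff are needed. The change should be made before the first Phase II subject, because ratings given in sight of the key cannot be corrected afterwards.

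### Phase II item 7 asks about difficulty in using the device but offers discomfort answers, so a scored point has an ambiguous meaning

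*Combined protocol and SAP*

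**What the plan says.** The Phase II sheet in Section 16 (Step 2) ends with two self-assessment items. Item 6 asks "Did you experience discomfort with the SaliPen in your mouth" and item 7 asks "Did you experience difficulties in using the SaliPen". The same answer list is printed beside each: "1- Severe discomfort 2- Moderate discomfort 3- No discomfort".

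One scoring note covers both items: "Success (1) is meant if options 2 or 3 were chosen", and "Failure (0) is meant if option 1 was chosen". Both count toward the total, which the sheet gives as "Total questions/tasks/self-assessments: 7", with at least 6 points needed to pass.

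Section 13 lists reporting of significant discomfort as Phase II Task 6 and reporting of significant difficulties in use as Task 7. It sets an 85% pass mark for each Phase II participant and requires 85% of participants to pass each phase. Section 15 also asks the two questions separately, with no answer options. Section 6 sets Phase II enrollment at 16.

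**The concern.** The question and its answers concern different things. A participant who struggled to operate the device but felt no discomfort has no fitting option. The literally true choice is the third one, which scores as success. A participant who felt severe discomfort but handled the device easily could mark option 1 twice and lose two points for one complaint. Other participants will follow the question and read the options as grades of difficulty. The completed sheet would not show which reading was used.

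Item 7 is the only scored item for Task 7 and feeds the participant pass mark, hence the Phase II success rule. The study is a summative usability evaluation, so self-reported difficulty is relevant evidence, and an answer recorded on the wrong scale cannot be reinterpreted reliably afterwards.

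**Working it through.** **The plan's own figures.** Participant pass mark: 0.85 × 7 = 5.95, so 6 of 7 (6/7 = 0.857 passes, 5/7 = 0.714 fails). This agrees with the sheet. Phase rule: 0.85 × 16 = 13.6, so 14 of 16 (14/16 = 0.875 passes, 13/16 = 0.8125 fails).

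**When item 7 matters.** A participant may lose one point and still pass. Item 7 therefore decides the result only if exactly one of items 1–6 has failed.

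**Worst case: the item 7 answer simply repeats item 6.**
- *Wrong pass.* One of items 1–5 failed, severe difficulty, no severe discomfort. Correct score 5/7 (fail); recorded score 6/7 (pass).
- *Wrong fail.* Items 1–5 all correct, severe discomfort, no severe difficulty. Correct score 6/7 (pass); recorded score 5/7 (fail).

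**Illustration under assumed rates.** The documents give none of these. Let p be the failure probability on each of items 1–5, d the probability of severe discomfort, f the probability of severe difficulty, and q the share of respondents who repeat item 6. Items are taken as independent.

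- A = (1−p)^5 (items 1–5 all correct); B = 5p(1−p)^4 (exactly one failed)
- Correct pass rate = A(1−df) + B(1−d)(1−f)
- Wrong pass = q·B(1−d)f; wrong fail = q·A·d(1−f)
- Recorded pass rate = correct pass rate + wrong pass − wrong fail
- Phase II probability = P(Binomial(16, pass rate) ≥ 14)

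For p = 0.10, A = 0.5905 and B = 0.3281. With d = 0.02 and f = 0.10:
- Correct pass rate = 0.5905 × 0.998 + 0.3281 × 0.98 × 0.90 = 0.879
- At q = 1, wrong pass = 0.3281 × 0.98 × 0.10 = 0.0321
- At q = 1, wrong fail = 0.5905 × 0.02 × 0.90 = 0.0106
- Recorded pass rate = 0.879 + 0.0321 − 0.0106 = 0.900

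| p | d | f | Pass rate, correct → q = 1 | Phase II probability, correct → q = 1 | At q = 0.25 |
|---|---|---|---|---|---|
| 0.02 | 0.02 | 0.02 | 0.992 → 0.976 | above 0.999 → 0.994 | 0.999 |
| 0.10 | 0.02 | 0.10 | 0.879 → 0.900 | 0.694 → 0.790 | 0.719 |
| 0.10 | 0.10 | 0.02 | 0.879 → 0.827 | 0.694 → 0.458 | 0.634 |

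In the third row, at q = 1, wrong passes are 0.0059 and wrong fails 0.0579. With q = 0 nothing changes in any row.

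**The case against.** The strongest reply is that the intended meaning is plain. The item 7 question, the participant guide and Task 7 all name difficulty, and Section 5.2 says subjects will be asked about ease of use. Item 6 has just asked about discomfort, so repeating that answer is the less natural reading, and severe/moderate/no works as a ladder for either construct. Section 15 describes the questionnaire as interviewer-administered, and Section 13 says "The evaluator will be a member of the study team", so staff can clarify. Correct use is scored mainly by items 1–5, which are untouched. On this view it is a form-wording slip, and the larger shifts in the table need every respondent to ignore the question.

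Much of this stands. The intended construct is clear from the rest of the document, q = 1 is a worst case, and milder assumptions give small shifts. With p = d = f = 0.05, q = 0.25 moves the Phase II probability only from 0.968 to 0.955, and q = 0.10 only to 0.963.

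Independence is also unsupported. If discomfort and difficulty had equal rates and always occurred together, repeating item 6 would misclassify nobody. With the unequal rates in the table, maximum overlap cuts total misclassification from 4.3% to 2.6% in the second row and from 6.4% to 4.7% in the third, but does not remove it. Nor must the net effect shrink. With full nesting, the correct pass rate in both rows is 0.5905 × 0.98 + 0.3281 × 0.90 = 0.874, giving a Phase II probability of 0.672. The recorded figures remain 0.790 and 0.458, so the upward shift grows (0.118 against 0.096) while the downward shift shrinks (0.214 against 0.236).

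The reply does not repair the form. The self-assessment block tells the participant to mark the option that applies, and the scoring note attaches the point to that option. No script tells staff how to resolve the mismatch, so any clarification would be ad hoc and could vary between participants.

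**Conclusion.** The concern holds. The mismatch is in the current text and touches a scored item that feeds the success rule. It is a measurement fault on the form; the pass marks, sample size and descriptive analysis are not in error.

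The consequence is bounded: item 7 can change a participant's result only at the one-failure boundary, and only if the answer would have differed under correct wording. The effect on the 14-of-16 threshold could be nil, slight or material, in either direction. The probabilities above illustrate sensitivity and do not predict a result, because the failure rates, independence and the share repeating item 6 are all assumptions. The wording error itself is certain. It should be corrected before the form is used, but it does not undermine the design.

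**What to change.** Before the first Phase II participant is scored, replace the item 7 options with: 1 – Severe difficulty; 2 – Moderate difficulty; 3 – No difficulty. Keep the existing note that option 1 is a failure and options 2 and 3 are successes.

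The seven items, the 6-point pass mark, the 14-of-16 requirement, the sample size and the analysis all stay as they are. The cost is one line on the form. If the protocol already has IRB approval, Section 14.4 requires approval of the amendment before it is implemented.

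Correcting it later is harder. If item 7 were discarded as uninterpretable, the 85% rule on six items would need 0.85 × 6 = 5.1, hence 6 of 6 (5/6 = 83.3%), which removes the one-point allowance the plan now gives.
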